1.2. Schedule of Assessments (SoA)

Procedure	Screening	Baseline	Assessments during hospitalisation	Primary endpoint Part A	Core secondary end point	Primary endpoint Part B	End of study/Early withdrawal
Day ± window		1	Day 3, 5, 8 (all ±1 day), then weekly (±3 d), or until discharge	15±3	29±3	61±7	91±14
Screening for eligibility¹							
Review SARS-CoV-2 laboratory results	X						
Informed consent	X						
Allocation to EU-SolidAct Part A or B by WHO disease stage ²	X						
Baseline procedures							
Demographics and medical history	X	X					
Randomization		X					
Standard of care (SoC) ³		X					
Study intervention		X	Note doses given				
Safety laboratory							
Safety biochemistry ⁴	X	(X)	X	X ⁵	X ⁵	X ⁵	X ⁵
Pregnancy test		X					
Study procedures							
Vital signs including SpO ₂		X	X	X ⁵	X ⁵	X ⁵	X ⁵
Review oxygen therapy ⁶		X	X	X ⁵	X ⁵	X ⁵	X ⁵
Review WHO stage ⁷		X	X	X ⁵	X ⁵	X ⁵	X ⁵
Concomitant medication		X	Note changes daily until discharge, note on occurrence	X ⁵	X ⁵	X ⁵	X ⁵
AE and SAE evaluation				X ⁵	X ⁵	X ⁵	X ⁵
PROM							X
Endpoints assessment							
Endpoint assessment ⁸		X	X	X	X	X	X
Biobanking (level II)							
Serum, EDTA Plasma, Whole blood		X	Day 3, 8, 15, 22 (all ±1) or until discharge before D22				
Naso/oropharyngeal swab		X	Day 3, 8, 15 (all ±1) or until discharge before D15				
Add-on studies (level III)							
Biobanking, other material		X	Add-on sub protocols				
Radiology		X	Add-on sub protocols				
Organ function		X	Add-on sub protocols				
PROM		X	Add-on sub protocols				

Modular data capture according to level of commitment (level I, level II, level III). Assessments in level I are mandatory. Biobanking (level II) is necessary for virological end points. Add-on sub-studies (level III) will be developed in collaboration with participating sites, developing common standardised procedures for additional biobanking, radiology and organ function.

1. Refer to chapter 8 for details. Screening/baseline assessments should be performed prior to study drug administration.
2. See separate table 4.1 for WHO stage and allocation to EU-SolidAct Part A (moderate disease) or B (severe disease).
3. Standard of Care (SoC) details, including medication.

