6.3. Measures to Minimize Bias: Randomization and Blinding

In addition to receiving SoC, all participants will be centrally assigned to randomized study interventions in the eCRF. When the participant has been deemed eligible for randomization, baseline information will be entered and then the participant will be randomised. Participants will be randomly assigned in an equal ratio between the intervention or comparator arms they are eligible for. Randomization will be computer-generated in permuted random-sized blocks with stratification. The stratification factors are shown in the table below. Randomization will be done at the baseline visit (day of study treatment initiation). For placebo-controlled interventions, the arm will not be revealed. Further details will be given in the intervention-specific protocol.

Table 6.3: Stratification factors of EU-SolidAct

EU-SolidAct Part A Moderate disease	EU-SolidAct Part B Severe disease

 - Centre - Need for oxygen at baseline (yes/no) 	
 - Centre - Previous entry in Part A (yes/no) - High flow oxygen or NIV vs mechanical ventilation/ECMO at baseline

Stratification by emerging treatment in SoC should be considered when these arise. Participants in EU-SolidAct Part A may undergo a second randomization at any point after being first randomized if they deteriorate and switch from moderate to severe/critical disease (EU-SolidAct Part B).

The second randomization will proceed as follow:

1. The informed consent form will cover both Part A and B. Thus, there will be no separate consent for the second randomization.

2. When a participant in Part A progresses and is eligible for Part B, the participant is screened against all intervention-specific protocols eligibility criteria. If the participant is eligible for at least one of the Part B interventions, the participant is randomised to one of the available interventions plus SoC or SoC alone.
3. The allocated treatment in Part A is continued unless instructed otherwise in the corresponding intervention-specific protocol, or by the discretion of the treating physician.

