The following assessments should be performed to determine eligibility requirements as specified in the inclusion and exclusion criteria:

- Register and review the positive SARS-CoV-2 test result
- Register and review SpO₂ measurement
- Register and review need for oxygen therapy, see section 8.1.2.
- Register and review prior and concomitant medication for allergies or contraindications to investigational medicinal products according to intervention-specific sub-protocol(s) eligibility criteria
- Register and review medical history for contraindications according to intervention-specific sub-protocol(s) eligibility criteria

- Register and review any other information according to intervention-specific sub-protocol(s) eligibility criteria

Once the patient is found to be eligible, go through the consent form with the patient and obtain informed consent.

Baseline procedures (Day 1):

After screening and obtaining informed consent, enter baseline data in the eCRF and randomize the patient (see section 6.3. for randomization procedure) as soon as possible after screening.

If participant is eligible for Part A include in Part A, if eligible for Part B include in Part B.

If not already collected as part of the intervention-specific sub-protocol assessment of eligibility criteria, collect the following information:

- Focused on medical history, including the following information:
 - Day of onset of COVID-19 symptoms
 - Day of hospitalization
 - History of chronic medical conditions and risk factors related to developing a severe COVID-19 disease: chronic pulmonary diseases (obstructive pulmonary disease, interstitial pulmonary disease, other), cardiovascular diseases (heart failure, coronary artery disease, other), kidney disease, liver disease, diabetes mellitus, hypertension, smoking, cancer, autoimmune diseases, immunodeficiency (HIV infection, primary immunodeficiency, other), neurological diseases
 - History of vaccination against COVID-19
 - History of prior infection
- Demographics (age, sex, country of birth)
- Register SoC details
- Register other concomitant medication than SoC if not already collected during screening. See details in section 6.8.
- Clinical Safety Laboratory Tests including pregnancy test for women of childbearing age, see section 8.3.5 and Appendix 2.
 - if more than 24 hours since screening, repeat blood samples for safety before first dose of study medication

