9.3.2. Primary endpoint(s) analysis

The primary endpoint for Part A is the occurrence of disease progression, defined as a progression of disease state from moderate (WHO scores 4-5) to severe/critical (WHO score 6-9) or death within 14 days, and the primary endpoint for Part B is the occurrence of death within 60 days. The Kaplan-Meier estimate will be used to estimate the disease progression rates. Kaplan-Meier curves will be plotted for the primary endpoints. We will calculate the Cochran-Mantel-Haenszel treatment difference and the 95% associated confidence interval in

the percentage of participants with disease progression (i.e., study intervention group response rate minus control group response rate) adjusted for the stratification factors of the randomization. The analyses may also be adjusted for other prognostic factors as sensitivity analyses. If the primary analysis adjusted for centre becomes unstable or non-identifiable due to small strata, adjustment by country will be done instead. The effect of study intervention will also be assessed using a time-to-event regression model with treatment group and adjustments for stratification factors.

The validity of the proportionality assumption will be evaluated and tested. Efforts to minimize lost to follow-up will be considerable. However, small amounts of missing data may occur. In such cases, participants without final outcome data will be censored at the date of last information. Sensitivity analyses will be conducted assuming all participants lost to follow-up progressed in both arms at time of censoring (worst case imputation), or none progressed and did not meet the primary endpoint (best case imputation). These sensitivity analyses will be fully defined in the statistical analysis plan (SAP).

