9.5. Sample Size Determination

9.5.1. Phase 3 General Considerations

In the DisCoVeRy (NCT04315948) and Nor-Solidarity (NCT04321616) trials, the proportion of patients with moderate disease at inclusion in achieving disease progression at day 14 and those with severe disease in achieving death at day 60 are shown in

Table 9.1 below.

Table 9.1 Event rate on SoC patient in Discovery and Nor-Solidarity trials

	Discovery	Nor- Solidarity	Nor-Solidarity
	(included: July- October 2020)	(included before 1st July 2020)	(included after 1st July 2020)
14-day rate of progression in moderate patients	13.1% [7.5-22.4]	13.5% [9.8-22.8]	20.5% [7.6-31.5]
28-day mortality in severe patients	9.7% [3.7-24.3]	5.1% [1.4-8.8]	9.1% [0.2-17.2]

According to numbers published by Santé publique France on December 29, 2020 there were 770 deaths out of 4411 (17.5%) patients admitted in ICU in France, suggesting a slightly higher rate compared to the autumn numbers in Discovery and Nor-Solidarity.

Based on these data, we assumed a cumulative probability of disease progression of 15% at 14 days in the SoC group for Part A (moderate disease) and mortality at 15% at 60 days for Part B (severe disease).

The sample size and power calculations were made using the statistical software package nQuery Advanced, using the two sample Log-Rank test module (Version 8.6.1.0), based on the primary efficacy estimand and its endpoint. The results are presented in Table 9.2 and Table 9.3 below.

Assuming a 15% progression for the SoC group in Part A and a 2-sided type-1 error rate of 5% and using the Log-Rank test, the study will have over 90% power under a sample size of 924, 521 and 378 per arm to detect a treatment difference of 5%, 6.5% and 7.5% respectively. We hypothesize that a treatment difference in progression rates at day 14 of 5% seems achievable. Therefore, we plan to enrol 950 participants per arm, considering potential dropouts before the assessment of the primary endpoint at day 14.

Table 9.2: Sample size calculation for EU-SolidAct Part A superiority trial

	Scenario 1	Scenario 2	Scenario 3
Outcome (Disease progression at day 14)			
Hypothesized event rate with SoC	15%	15%	15%
Expected event rate with intervention	10%	8.5%	7.5%
Type I error (two-sided)	0.05	0.05	0.05
Power	90%	90%	90%
Hazard ratio (HR)	0.648	0.547	0.48
N per group	924	521	378
Total number of events required	224	115	78

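### Section 9.3.2 leaves baseline age out of the primary risk difference and the time-to-event model, so a small amount of precision is given up; the planned analysis remains valid

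*Protocol*

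**What the plan says.** In section 9.3.2 the primary comparison is a CMH difference in event proportions "adjusted for the stratification factors of the randomization". The treatment effect is also to be assessed with a "time-to-event regression model with treatment group and adjustments for stratification factors". Neither model contains any other baseline variable. Further adjustment is permitted but not required, and only in a supporting role: "The analyses may also be adjusted for other prognostic factors as sensitivity analyses". The factors are not listed.

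Table 6.3 gives the strata. Part A uses centre and "Need for oxygen at baseline (yes/no"). Part B uses centre, previous entry in Part A, and "High flow oxygen or NIV vs mechanical ventilation/ECMO at baseline". Age is in neither list.

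Age is nevertheless available. The Day 1 baseline procedures in section 8 include "Demographics (age, sex, country of birth"), and the Schedule of Assessments (section 1.2) places demographics at screening and baseline and notes that "Assessments in level I are mandatory". Section 9.3.4 uses age as a planned subgroup, split at 65 years.

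For the sample size (section 9.5.1), "we assumed a cumulative probability of disease progression of 15% at 14 days in the SoC group for Part A", with the same 15% for 60-day mortality in Part B. The target is 10% with the intervention, by a two-sample log-rank test without covariates.

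**The concern.** Adjusting for a baseline variable that predicts the outcome reduces the variance of the treatment comparison without biasing it. It also removes the effect of a chance imbalance in that variable. Age is measured before treatment, costs nothing more to collect, and matters enough to the sponsor to be a planned subgroup. Yet the wording of section 9.3.2 keeps it out of both main models. This is a choice that the protocol states, not a detail left open: an analysis plan that followed the section as written would keep age in sensitivity analyses.

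What is at stake is some power and some interval width. It would count most in Part B if mortality is lower than the assumed 15%. Table 9.1 shows 28-day mortality of 5.1% to 9.7% in severe patients. The time point differs from the 60-day endpoint, and section 9.5.1 also cites 17.5% among French ICU admissions, so a lower rate is a possibility to test and not an established fact.

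**Working it through.** **1. Reproducing the plan's figure.** Inputs from section 9.5.1 and Table 9.2: 15% vs 10%, two-sided 5%, 90% power, equal allocation.

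- Hazard ratio: ln(0.90)/ln(0.85) = 0.648, as stated.
- Freedman events: (1.960 + 1.282)² × [(1 + 0.648)/(1 − 0.648)]² gives 231. Then 231/(0.15 + 0.10) = 924 per arm, as stated.
- Schoenfeld events: 4 × (1.960 + 1.282)²/(ln 0.648)² gives 224, the stated event count.

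None of this uses a covariate, so the stated size does not depend on age adjustment.

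**2. Unadjusted power on the risk-difference scale.** Power = Φ{[d√n − 1.96√(2p̄(1 − p̄))]/√(p₁(1 − p₁) + p₂(1 − p₂))}, where d = p₁ − p₂ and p̄ is the mean of the two risks.

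- 15% vs 10%, n = 924: (0.05 × 30.40 − 1.96 × 0.4677)/0.4664 = 1.293, power 90.2%.
- 10% vs 6.6%, n = 950: (0.034 × 30.82 − 1.96 × 0.3902)/0.3894 = 0.727, power 76.7%. The 6.6% is the plan's hazard ratio applied to a 10% control risk: 1 − 0.90^0.648 = 0.066.

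**3. Outcome variance explained by age.** The documents give neither an age effect nor an age SD. Assumed range: odds ratio 1.3 to 2.0 per 10 years, SD 12 to 15 years, age normal, logistic risk. The log odds ratio per SD is ln(OR) × SD/10, which is 0.315 at the low end (odds ratio 1.37 per SD) and 1.040 at the high end (2.83 per SD). R² = Var[p(age)]/[p̄(1 − p̄)], taken at the pooled risk of each scenario.

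- p̄ = 12.5%: R² = 0.011 to 0.113.
- p̄ = 8.3%: R² = 0.008 to 0.089.

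**4. Power with age in the model.** Replace n by n/(1 − R²) in step 2.

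| Scenario | Unadjusted | Low end | High end |
|---|---|---|---|
| 15% vs 10%, 924 per arm | 90.2% | 924/0.989 = 934; 90.5% | 924/0.887 = 1042; 93.2% |
| 10% vs 6.6%, 950 per arm | 76.7% | 950/0.992 = 958; 77.0% | 950/0.911 = 1043; 80.4% |

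**5. Check by simulation.** Trials with 924 per arm at 15% vs 10%, 3,000 per setting. The unadjusted risk difference was compared with the standardised risk difference from a logistic model containing one standardised covariate. Adjusted power is from the Wald test of the treatment coefficient.

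| Odds ratio per SD | Variance ratio (adjusted/unadjusted) | Power unadjusted | Power adjusted |
|---|---|---|---|
| 1.3 | 0.994 | 90.7% | 90.6% |
| 1.6 | 0.976 | 90.9% | 91.3% |
| 2.0 | 0.955 | 89.9% | 91.4% |
| 2.5 | 0.904 | 90.2% | 92.6% |

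The mean adjusted difference stayed at −0.050 throughout, so adjustment introduced no bias. A weak age effect brings no visible gain; a strong one brings about 2.5 points.

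**The case against.** The strongest reply is that nothing here is an error. Adjusting for the randomization strata is a standard, valid analysis that matches the design, and the sample size was set without covariates. That stands: the point concerns efficiency only.

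Second, the gain is assumed and gross. R² in step 3 is computed as if age were the only covariate, whereas the plan already adjusts for centre and for oxygen need or ventilation. Only what age adds beyond these counts. That also stands, so the figures are upper limits. The top of the range needs an odds ratio of 2.83 per SD.

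Third, naming sensitivity covariates is ordinary work for the statistical analysis plan. That is right for the list of factors, but it does not answer the point, because section 9.3.2 itself confines all further adjustment to sensitivity status.

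Two stronger readings are tempting and not supported. A reader might infer that the optional wording lets the sponsor pick a favourable adjusted result after seeing the data. But the CMH difference is already the primary result, other adjustments are labelled sensitivity analyses, and section 9 has the analysis plan finalised before database lock. A reader might also put the gain in the low-mortality scenario at up to 82%. That comes from carrying the R² for a 15% risk (up to 0.124) into a scenario with a pooled risk of 8.3%. At the right risk the ceiling is about 80.4%.

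**Conclusion.** The point holds as a modest loss of efficiency that could be avoided without new data. Section 9.3.2 keeps age out of both main models although it is collected at baseline and is not a stratum. The planned analysis is unbiased and the 924 per arm stands.

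Under the assumed age effects, the gain forgone is about 0.3 to 3.0 percentage points of power at 15% vs 10%, and about 0.3 to 3.7 points at 10% vs 6.6%, less whatever the strata already explain. The direction is secure if age predicts the outcome. The size rests on an odds ratio and an SD that the documents do not give, and at the low end it is negligible.

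**What to change.** In section 9.3.2, prespecify age as a continuous covariate, together with the stratification factors, in the time-to-event regression already planned.

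Name one risk difference as primary in advance. The preferable choice is the standardised risk difference from a logistic model with treatment, stratification factors and age, with the CMH difference reported as supportive. Adding age bands to the CMH strata is not a good route, because the section already foresees unstable results from small centre strata. Its fallback from centre to country can apply to the logistic model too.

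If the sponsor prefers to keep the CMH difference as primary, the section should say that the age-adjusted estimate is supportive and that the precision gain applies only to it. Reporting two risk differences without saying which decides would leave the primary interval no narrower and add an ambiguity.

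Cost: no new data and a little more analysis code. The primary estimate would rely on a regression model, and the hazard ratio would become conditional on age.

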9.3.3. Secondary endpoint(s) analysis

The occurrence of disease progression, defined as a progression of disease state from moderate (WHO score 4-5) to severe/death (WHO score 6-10) or from severe (WHO score 6-9) to death within 28 days will be estimated using Kaplan-Meier estimates. The same methodology will be used for these endpoints than the one described in section 9.3.2.

The median time from randomization to sustained recovery, with sustained recovery defined as being discharged from the index hospitalization, followed by being alive and home for 14 consecutive days within 90 days will be estimated using the Kaplan-Meier method. The log-rank test will be used to compare each study intervention and the control survival functions. Participants will be censored at the date of lost to follow-up or at the 90th day after randomization when the participant has not achieved the event before. The effect of study intervention on the time to sustained recovery will also be assessed using Cox regression model with treatment group and adjustments for stratification factors.

The median time from randomization to first hospital discharge within 90 days will be analysed with the methodology described above.

Continuous endpoints will be analysed using analyses of covariance adjusted by stratification factors in the randomization and baseline value if applicable, or appropriate (generalised) linear mixed model with random intercept and possibly slope for repeated measures.

For the analysis of disease state on a 5-point scale a proportional odds model will be used. The hypothesis test will be based on a test of whether the common odds ratio for treatment is equal to one. Model fit will be evaluated using a goodness-of-fit likelihood ratio test. The distribution of severity results will be summarized by treatment arm as percentages. The validity of the proportionality assumption will be evaluated and tested.

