3.2. Phase 2 Trial Objectives and Endpoints

In phase 2 exploratory trials, the default primary objective for both part A and B is to explore the effect of the intervention on respiratory dysfunction, in line with the RECOVERY platform trial protocol. The same objectives and endpoints as for phase 3 trials should be considered, but the final selection, ranking and frequency of assessments will be given in the intervention-specific sub-protocols according to the intervention and the disease stage at inclusion. In addition, more specific end points should be specified according to the characteristics and mode of action of the IMP, and according to emerging variants of SARS CoV2.

Table 3.2 Phase 2 objectives and corresponding endpoints

Objectives	Endpoints
Primary	
The primary objective is to explore the effect of therapeutic interventions on respiratory dysfunction	SpO ₂ /FiO ₂ -ratio at day 5
Secondary	
Secondary objectives are selected from the objectives in Table 3.1 as relevant for the IMP (based on the mode of action)	Corresponding endpoints are selected from Table 3.1 , possibly with increased frequency of assessment

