9.5.2. Phase 2 General Considerations

Based on unpublished data from 8500 patients with COVID-19 as described in the RECOVERY protocol (<https://www.recoverytrial.net/files/recovery-protocol-v14-0-2021-02-15.pdf>), assuming a mean (standard deviation) SF-ratio of 3.3 (1.7) at day 5, and a correlation between an individual's baseline and day 5 SF-ratio of 0.5, randomization of 400 participants will provide 90% power at a two-sided 5% significance level to detect a difference in SF-ratio of 0.5 (the chosen minimum clinically meaningful difference [which is similar to the difference in 1 point on the WHO ordinal scale]), even if 10% of participants discontinue study treatment before day 5.

10. Supporting Documentation and Operational Considerations

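### The 90% phase 2 power requires adjustment for baseline SF-ratio, but section 9.3 does not bind the phase 2 primary comparison to it and names an unadjusted test for all outcomes

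*Protocol*

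**What the plan says.** All references are to the protocol.

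- **Section 3.2 (Table 3.2)** makes the SpO₂/FiO₂ ratio at day 5 the default phase 2 primary endpoint.
- **Section 9.5.2** gives the phase 2 sample size. It takes a day-5 mean of 3.3 with SD 1.7, together with "a correlation between an individual's baseline and day 5 SF-ratio of 0.5". The target difference is 0.5, with an allowance for 10% stopping study treatment before day 5. It concludes that "randomization of 400 participants will provide 90% power at a two-sided 5% significance level".
- **Section 9.3.1** says that, for every outcome, each intervention group is compared with control. It assigns the Mann-Whitney test to continuous variables and mentions no covariates.
- **Section 9.3.2**, on the primary endpoint analysis, deals with progression within 14 days (Part A) and death within 60 days (Part B). It does not mention the SF-ratio.
- **Section 9.3.3**, on secondary endpoints, holds the only model text for continuous endpoints, in one sentence with two branches. One branch is "analyses of covariance adjusted by stratification factors in the randomization and baseline value if applicable". The other branch reads "or appropriate (generalised) linear mixed model with random intercept and possibly slope for repeated measures".
- **Section 1.2, the baseline procedures in section 8, and section 8.1.2** schedule SpO₂ and oxygen therapy on Day 1 and say how FiO₂ is recorded or estimated. A baseline SF-ratio is therefore available for most participants.

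**The concern.** A baseline-to-day-5 correlation enters a power calculation only through an analysis that uses the baseline value, so section 9.5.2 presupposes such an analysis. The analysis sections do not commit to one for the phase 2 primary endpoint. The section where the commitment belongs is silent on phase 2. The test named for all outcomes is unadjusted. The one suitable model sits under secondary endpoints, with baseline conditional in one branch and unmentioned in the other.

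An analyst could follow section 9.3.1 to the letter, or fit a model without baseline, and stay within the protocol. The phase 2 comparison would then have about twice the type II error that section 9.5.2 implies.

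**Working it through.** **Inputs** (section 9.5.2 unless noted): SD 1.7; difference 0.5; correlation ρ = 0.5; two-sided α = 0.05; 400 randomised, 200 per arm (section 1.1), equal allocation (section 6.3). Treating the 10% allowance as lost observations gives 180 per arm.

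**Formula:** power = Φ(0.5 / (SD\* × √(2/n)) − 1.96), where SD\* is the standard deviation that applies to the analysis.

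**1. The plan's own figure.** With baseline adjustment, SD\* = 1.7 × √(1 − 0.5²) = 1.472. At n = 180 the standard error is 1.472 × √(2/180) = 0.155. Then 0.5/0.155 = 3.22, and Φ(3.22 − 1.96) = 89.7%. This reproduces the stated 90%.

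**2. Baseline omitted.** SD\* = 1.7 and the standard error is 1.7 × √(2/180) = 0.179. Then 0.5/0.179 = 2.79, and Φ(2.79 − 1.96) = 79.7%. A change score does no better: its variance is 2(1 − 0.5) = 1 times the raw variance.

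**3. Mann-Whitney.** Under normality its asymptotic efficiency relative to the t-test is 3/π = 0.955. The effective n is 180 × 0.955 = 172 per arm, which gives 77.8%.

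| Day-5 comparison | 180 per arm | 200 per arm |
|---|---|---|
| Baseline-adjusted | 89.7% | 92.5% |
| No baseline, or change score | 79.7% | 83.7% |
| Unadjusted Mann-Whitney (normality) | 77.8% | 82.0% |

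**4. Mixed model.** Assume a random-intercept covariance with correlation 0.5 between all visits, complete data, arm-by-day terms and 180 per arm:
- days 3, 5 and 8 without baseline, day-5 contrast: 79.7%. The random intercept does not stand in for baseline, and the contrast is the raw mean difference;
- Day 1 added as an outcome with arm means free at baseline, contrast in change: 79.7%;
- Day 1 added as an outcome with equal arm means at baseline: 89.7%;
- effect averaged over days 3, 5 and 8 without baseline: 92.7%. This is a different quantity from the day-5 endpoint and assumes a difference of 0.5 at every visit.

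**5. Sample size without baseline.** For 90% power, 243 evaluable per arm would be needed, or 243/0.9 = 270 randomised per arm.

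**6. Sensitivity to the 10% allowance.** Section 9.5.2 speaks of stopping treatment, and section 7.1 keeps such participants in follow-up. If all 200 per arm are analysed and those who stop contribute no effect (an assumption), the difference is 0.9 × 0.5 = 0.45. Power is then 86.4% with baseline and 75.4% without. The gap is again about 11 points.

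**The case against.** A reader might infer that the protocol plans a mixed model without baseline, or that its mixed model has only about 80% power. The documents support neither. The mixed-model clause is silent on baseline, and the first half of the same sentence names ANCOVA with the baseline value, which is the analysis that reproduces 90%. A mixed model that uses baseline properly also keeps 89.7%. The figure of about 80% belongs to the omission of baseline, not to the model class.

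Other points on that side carry weight:

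- The mixed-model branch is for repeated measures, while the phase 2 primary endpoint is a single day. SF-ratio at days 3, 5 and 8 is a separate secondary endpoint (1.6 in Table 3.1). ANCOVA is the natural reading for day 5.
- Baseline is plainly applicable to SF-ratio. The qualifier has a proper use for endpoints with no baseline, such as the Day 91 questionnaire at level I.
- Oxygen need (Part A) and ventilation mode (Part B) are stratification factors and are related to SF-ratio. Adjusting for them alone should recover some precision, by an amount the documents do not allow one to calculate.
- Section 9 calls itself a summary, and covariate detail commonly belongs in the SAP, which is not shown. Phase 2 is also described as exploratory.

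These points narrow the concern but do not remove it. Section 9.3.1 does more than omit detail: it states an unadjusted test for all outcomes. For the phase 3 primary endpoints, section 9.3.2 then gives a specific analysis. For the phase 2 primary endpoint, no primary-analysis text does so, and the protocol does not say that section 9.3.3 prevails.

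**Conclusion.** The point holds as a mismatch between the stated power and the stated analysis. The 90% in section 9.5.2 is correct for a baseline-adjusted day-5 comparison. The protocol does not bind the phase 2 primary endpoint to that comparison, and the test it names for all outcomes would not deliver the power.

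At 180 per arm the shortfall is 10 points if baseline is omitted (89.7% to 79.7%) and about 12 points for the Mann-Whitney test (77.8%). Type II error rises from about 10% to between 20% and 22%.

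The figures rest on the plan's SD, difference and correlation, and on reading the 10% as lost observations. The Mann-Whitney figure also assumes normality; the documents do not give the shape of the SF-ratio distribution, and another shape could move it either way. The mixed-model figures assume equal correlation of 0.5 between visits. The 79.7% assumes no help from the stratification factors.

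Nothing here shows that the phase 2 sample size is too small.

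**What to change.** Add to section 9.3.2 that the phase 2 primary endpoint is compared at day 5 by ANCOVA, or by a mixed model for days 3, 5 and 8 with arm-by-day terms and the day-5 contrast as the test. In either case the model includes baseline SF-ratio and the stratification factors. State that this takes precedence over the general Mann-Whitney sentence in section 9.3.1.

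Keep the conditional wording on baseline in section 9.3.3 for endpoints with no Day 1 measurement.

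The cost is one or two sentences; no new data and no change in sample size are needed. The small downside is that some participants will have no calculable Day 1 ratio. For example, section 8.1.2 collects no further oxygen data on ECMO. The text should say how they are handled, so that they do not drop out of the full analysis set by default.
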